1.0 PROJECT SUMMARY/ABSTRACT

Alcohol use disorder (AUD) affects millions and is one of the leading causes of preventable death worldwide. In the US, pharmacotherapy for AUD is under-utilized; related to the fact that there are only three FDA-approved drugs to treat patients with AUD. These medications work well for some but have small to moderate effect sizes on drinking outcomes. The development of more efficacious pharmacotherapies for AUD is a top public health priority. A recent emphasis in psychiatric medication development is the use of reliable human laboratory measures of AUD dysfunction to test promising compounds to directly inform and power large-scale mechanistic clinical trials. PI [name] and Co-I [name] have developed an assay of stress reactivity that is robustly related to drinking behavior and AUD. This assay reflects a negative reinforcement model of AUD and is reliably captured in the lab using complimentary objective psychophysiological (i.e., startle eyeblink potentiation) and functional neuroimaging measures. Using this model, we have uncovered that suvorexant (SUV) – a dual receptor antagonist of the orexin system, FDA-approved for insomnia – acutely modifies our AUD target in healthy adults, while sparing changes in other markers of stress reactivity. Compelling animal and human evidence together suggest that the orexin system is critically involved in stress-related alcohol use. The overarching goal of this study is to systematically advance this line of work to uncover if, how, and for whom orexin antagonism modifies brain-behavior stress targets of AUD to inform and power future large scale clinical trials. The study is a targeted double-blind, between-subjects, randomized clinical trial design with repeat lab assessment. A total of eighty subjects with AUD will complete our psychophysiological stress paradigm at baseline. They will return to the lab days later to repeat the protocol following administration of a single dose of either 10mg SUV or placebo (40 subjects/arm). Participants are then instructed to take daily 10mg capsules of SUV or placebo for the next 4-weeks before returning for a post-treatment lab assessment. Daily reports of medication adherence, side-effects, sleep, alcohol use, and mood will be collected via smartphones.

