Novel preclinical research indicates that the hypocretin/orexin (ORX) hypothalamic neuropeptide system plays a pivotal role in alcohol abuse. In rodents, antagonism of ORX receptors prevents alcohol-seeking behavior and binge-like alcohol drinking, while preserving motivation for natural rewards¹⁹⁻²². ORX receptor antagonism also robustly reduces behavioral and psychophysiological stress reactivity to threat and pharmacological challenge²³⁻²⁴. ORX antagonism may therefore be an effective strategy for disrupting the negative reinforcement cycle of addiction. Remarkably, using a within-subjects, placebo-controlled design our prelim data indicates an acute dose of suvorexant (SUV) – an FDA-approved dual ORX receptor antagonist for insomnia – robustly reduces behavioral reactivity to U-threat in adults, while sparing changes in other psychophysiological markers of threat sensitivity less relevant to AUD. ORX antagonism selectively engages the U-threat target, providing compelling evidence it is a promising pharmacological treatment for individuals with AUD and high U-threat reactivity, who frequently engage in stress-related alcohol use^{22, 25-28}.

No prior study has measured stress-related ORX target engagement in humans to uncover how ORX antagonism can be leveraged to treat AUD. The overarching goal of the current study is to advance ORX translation to the AUD clinic using a proof-of-concept

double-blind, between-subjects, randomized clinical trial design with repeat lab assessment.

All subjects will complete three lab visits of psychophysiological data collection. A subset of 20 subjects per arm (40 total) will also complete our stress task during simultaneous startle and functional magnetic resonance imaging (fMRI), pre- and posttreatment. This design allows us to address if, how, and for whom ORX antagonism modifies brain-behavior stress targets to inform and power future large scale mechanistic clinical trials.

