Study Overview. The study is a double-blind, between-subjects, randomized clinical trial with a multi-session lab paradigm (see Figure 1). Participants will first complete an initial Screening Session where they will complete an assessment of study eligibility (described above), a clinical interview, and questionnaires. If participants are found to be eligible, they will be randomized to a treatment group (SUV or placebo) and protocol arm (BEHAVIOR or BRAINS Group). Those in the BEHAVIOR Group will complete electromyography (EMG)/electroencephalography (EEG) only and those in the BRAINS Group will complete EMG/EEG + fMRI.

Therefore, participants have a chance of being randomized to four different groups (20 participants/group): 1) BEHAVIOR - SUV; 2) BEHAVIOR - Placebo; 3) BRAINS - SUV; and 4) BRAINS - Placebo.

BEHAVIOR Group Overview:

Following the Screening Session, participants randomized to the BEHAVIOR group will come in-person to Lab Visit 1 where they will complete the psychophysiological stress paradigm and Alcohol Cue Reactivity EEG task. Days later, they will return to the lab for Visit 2 (Acute Drug Challenge) and repeat the protocol during their first dose of medication (placebo or 10mg SUV). Next, they will be instructed to take a 10mg dose of SUV (or placebo) each night before bed for 4-weeks. Daily online assessments of medication compliance, side-effects, alcohol use, mood, and sleep will be collected. During the final week of the protocol subjects will return for Lab Visit 3 to repeat the paradigm (dose taken night prior, as prescribed).

BRAINS Group Overview:

Following the Screening Session, participants randomized to BRAINS Group will complete the same procedures as above with the exception of completing two additional fMRI visits pre- and post-treatment. Therefore, participants will complete: Lab Visit 1 (EMG/EEG), Lab Visit 2 (fMRI), Lab Visit 3 (Acute Drug Challenge), four weeks of SUV (or placebo) administration with daily online assessments, Lab Visit 4 (EMG/EEG), and Lab Visit 5 (fMRI).

Screening. During the Screening Session, participants will complete an assessment of study eligibility, the Structured Clinical Interview for DSM-5 (SCID-5)³¹ with trained study staff, and a short battery of self-report questionnaires (see Table 1 and Table 2). Participants will be given the choice to complete the Screening Session online or in-person to accommodate potential limited access to the internet.

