Randomization, Blinding, and Dosing. A computerized stratified block randomization will assign subjects to a treatment group and protocol arm. The randomization will be stratified by biological sex. The research team and participants will be blind to medication assignment. The PI will have the ability to unblind if needed. OSU Investigational Drug Services (IDS) staff and CRC medical staff will be unblinded.

Participants will receive either placebo or suvorexant (Belsomra®; 10mg; Merck & Co). This dose was chosen because it is the lowest clinical dose for sleep and arousal-related outcomes. We used 10mg in our pilot project and found significant change in reactivity to U-threat without adverse reactions (Protocol#: 2020H0285).

Laboratory Tasks. Participants will complete a startle response to threat task at the EMG/EEG, fMRI, and Acute Drug Challenge Visits (described below). The same paradigm will be administered during the EMG/EEG and Acute Drug Challenge Visit. The fMRI task is analogous to the original design; however, shock is administered to the left foot to minimize potential scanner interference and individual shock levels are re-calibrated. During the tasks, we will collect psychophysiological measures including startle eyeblink potentiation. At the EMG/EEG visit a second task, Alcohol Cue Reactivity⁷¹ will be completed. These tasks are well-established, validated paradigms,

previously used in our laboratory for the past several years in both healthy and adults with AUD.

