Administration Timing. Peak plasma concentration for suvorexant is 2 hours post-ingestion. Therefore, participants will receive the drug (or placebo) at the CRC upon arrival. After 1.5 hours (90 minutes post ingestion), participants will be escorted to the laboratory for EMG/EEG testing. Laboratory assessments will occur during peak concentration, ~2 hours post-ingestion.

Self-Report Assessments During Acute Drug Challenge. Throughout the Acute Drug Challenge Visit standardized questionnaires will be used to assess mood states and subjective drug effects: (1) Karolinska Sleepiness Scale (KSS)⁶²; (2) Anxiety Visual Analog Scales (VAS)⁶³; and (3) Drug Effects Questionnaire (DEQ)⁶⁴; and Profile of Mood

States (POMS)⁶⁵. The KSS, VAS and DEQ will be collected immediately before capsule ingestion (Time 0), and approximately 30, 60, 90, 120, 150, 180, and 210, and 240 minutes afterwards. The POMS will be completed immediately prior to capsule ingestion (Time 0), and approximately 60 minutes, 120 minutes, and 240 minutes afterwards.

Vitals Signs Measurements During Acute Drug Challenge. Physiologic measures will be collected throughout the study visit: (1) Blood Oxygen (O₂) Saturation; (2) Heart Rate and (3) Blood Pressure will be taken before capsule ingestion (Time 0), and approximately 30, 60, 90, 120, 150, 180, and 210, and 240 minutes afterwards. Measurements will be performed at the CRC or in the PI's lab using portable blood pressure and finger oximeter. Measurements will be obtained using a finger oximeter and portable blood pressure cuff. Any participant who experiences excessive drowsiness, allergy symptoms, and/or adverse drug reactions will be assessed by the CRC and study physician and immediately withdrawn from the study as a safety measure.

Drug Trial and Monitoring. At the end of the acute challenge, subjects will be provided the rest of their prescription (SUV or placebo) in blister packaging, prepared by OSU IDS. The blister packaging will be labeled with each date of the protocol. Subjects will be directed to ingest one pill each night, as they get into bed (~30 mins prior to sleep time) to mitigate drowsiness, consistent with SUV's prescription.

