15.0 Aim 3. Does daily use of SUV change alcohol behavior, and is this change linked to brain-behavior U-threat change? Hypothesis 3a: Daily SUV will result in greater reductions in PHDD and DPDD compared with PBO. **Hypothesis 3b:** SUV-related changes in PHDD and DPDD will be greatest in those with higher U-threat reactivity. **Hypothesis 3c:** In all subjects, changes in brain-behavioral U-threat reactivity will correlate with changes in drinking behavior. For H3a, linear mixed models will be used to assess the impact of treatment arm (SUV vs. PBO) on changes in drinking behavior over the 4-week follow-up period (daily reports). If the assumptions of linear models are violated due to skewed residual errors, we will explore the use of Poisson and negative binomial generalized linear mixed models to model drinking behavior. For H3b, baseline startle potentiation to U-threat (and in secondary models, aINS, dACC, and BNST parameter estimates) will be entered as a covariate/predictor and we will test for a baseline startle to U-threat by treatment arm interaction on drinking behavior outcomes. Lastly, the hypothesis for H3c will be tested using a linear mixed model that includes magnitude of U-threat and P-threat reactivity (startle and brain, separate models), time, and treatment arm as predictors and PHDD and DPDD as the outcomes. We expect a startle by time interaction such that regardless of treatment arm, a change in U-threat reactivity will correspond to a change in drinking behavior.

Sample Size. Our key hypothesis testing involves treatment arm by session interactions on startle eyeblink potentiation. Assuming a medium to large effect size, which is supported by our preliminary data, a sample size of 40 individuals per treatment group would conservatively yield 91% power (a total sample size of 80 individuals). To account for potential screen-fails, participants requesting to drop out of the study, and the PI withdrawing participants due to meeting termination criteria, approval for 120 participants is requested.

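### Does the 91% power figure fail for the four-week test (H2a) because the preliminary data are acute-dose only?

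*Combined protocol and SAP*

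**What the plan says.** The Sample Size paragraph describes what is powered: "Our key hypothesis testing involves treatment arm by session interactions on startle eyeblink potentiation". It then states the assumption, "Assuming a medium to large effect size, which is supported by our preliminary data", and the result, "a sample size of 40 individuals per treatment group would conservatively yield 91% power (a total sample size of 80 individuals". It gives no numeric effect size, alpha, SD or session correlation.

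Two tests fit that description. Under Aim 1, H1 compares baseline with the acute challenge. Under Aim 2, H2a uses almost the same model with post-treatment as the second time point.

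The suvorexant preliminary data appear in three places:

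- 2.0 Background: "using a within-subjects, placebo-controlled design our prelim data indicates an acute dose of suvorexant (SUV", followed by the statement that reactivity to U-threat fell.
- 1.0 Project Summary: the drug "acutely modifies our AUD target in healthy adults".
- 6.0, Randomization, Blinding, and Dosing: "We used 10mg in our pilot project and found significant change in reactivity to U-threat without adverse reactions".

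The two tests differ in exposure. For the acute visit, Administration Timing in 6.0 says "Laboratory assessments will occur during peak concentration, ~2 hours post-ingestion". For the post-treatment visit, the BEHAVIOR Group Overview says "During the final week of the protocol subjects will return for Lab Visit 3 to repeat the paradigm (dose taken night prior, as prescribed".

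**The concern.** The plan treats a single dose and daily use as separate questions (Aims 1 and 2), yet one effect size and one body of evidence serve both. No section reports startle after repeated suvorexant dosing, or on the day after a dose. An effect seen at peak concentration after one capsule need not be the effect some weeks later, the morning after the last one. The word supported therefore seems to claim more for H2a than the documents show.

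What would be at stake is the reading of a null result. If H2a were negative and reported beside 91% power, a reader might take it as good evidence that daily suvorexant does not act on the target. The project summary says the findings will inform and power a larger trial, so such a misreading could carry forward.

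Two further differences between the pilot and the trial, healthy adults and a within-subject design, add little. They apply equally to H1. The change of population could act in either direction, since 2.0 Background reports greater U-threat reactivity in AUD. A within-subject design need not change the standardised effect either. The point rests on dosing duration and time since dose.

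**Working it through.** **Inputs.** From the Sample Size paragraph: 40 per arm, 80 in total, 91% power, an effect described only as medium to large. Assumed here, because the paragraph does not give them: two-sided alpha 0.05, all 40 per arm evaluable, equal SD of change at both follow-ups.

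**Can 91% be reproduced?** Not from stated inputs, since there is no numeric effect. It can be back-solved.

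*Change-score scale.* Two-sample t test on change, df = 2 × 40 − 2 = 78, noncentrality d × √(40/2) = 4.472 d.

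| d (SD of change) | Power |
|---|---|
| 0.5 | 59.8% |
| 0.634 | 80% |
| 0.747 | 91% |
| 0.8 | 94.2% |

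If medium and large are read as 0.5 and 0.8 on this scale, 91% falls inside the range, towards its upper end.

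*Repeated-measures f scale.* λ = f² × N × m / (1 − ρ) with N = 80, m = 2 sessions and F(1, 78). At f = 0.25, λ = 0.0625 × 160 / (1 − ρ) = 10 / (1 − ρ).

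| ρ | λ | Power |
|---|---|---|
| 0 | 10.0 | 87.8% |
| 0.105 | 11.17 | 91.0% |
| 0.3 | 14.29 | 96% |
| 0.5 | 20.0 | 99% |

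On this scale f = 0.25 already gives 91% at a low session correlation. The stated figure is attainable under either convention; the documents do not say which was used.

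**What if the four-week effect is smaller than the acute one?** The documents give no four-week effect, so the retained fraction k is hypothetical. Power for H2a:

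| k | Acute effect exactly d = 0.747 | f = 0.25, ρ = 0.3 | f = 0.25, ρ = 0.5 |
|---|---|---|---|
| 1.00 | 91% | 96% | 99% |
| 0.90 | 84% (d = 0.673) | 92% | 98% |
| 0.75 | 70% (d = 0.560) | 80% | 91% |
| 0.50 | 38% (d = 0.374) | 46% | 60% |

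The first column starts from the value that gives exactly 91%, so any loss falls below it by construction. The other two start higher: since λ = 20 d², f = 0.25 at ρ = 0.5 equals d = √(20/20) = 1.0 SD of change. Nothing in the documents selects a column.

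**Would a stated detectable difference be firmer?** At two-sided 0.05 it would be 0.63 SD for 80% power and 0.75 SD for 91%. Section 10.0 calls for Bonferroni correction without giving the number of tests. If the two key tests shared alpha (0.025 each), the values would be 0.70 and 0.81. Such a statement would therefore need its own assumption.

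**Does the contrast matter?** The paragraph names arm by session on potentiation, while Aim 1 expects a three-way interaction with task condition. If the U and P potentiation changes have equal SDs and correlate at 0.5, and P-threat shows no drug effect, the three-way d is 0.747 × (1 − 0) / √(2 × (1 − 0.5)) = 0.747, again 91%. This difference in wording does not show the figure to be wrong.

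**The case for a change.** The strongest case for a change is that the plan does more than assume an effect: it says the effect has support, and for H2a no described data supply it directly. Under the change-score assumptions, a four-week effect half of 0.747 would be missed about 62% of the time (100% − 38%). A few added sentences would correct the impression at almost no cost.

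The factual part stands. The support is direct for H1 and indirect for H2a, and the paragraph does not separate them. It is also true that the word conservatively has no listed input behind it.

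The rest is weaker. It is too much to say that nothing supports the H2a effect: the pilot used the trial's 10 mg dose and found a change in the same measure. Extrapolating from acute data is ordinary for a trial described as proof of concept. The paragraph opens its sentence by calling the effect an assumption. The pilot's figures belong to a separate protocol, so their absence here does not show that they are inadequate. No section plans to interpret a null H2a by citing 91% power, and the width of the interval from the planned H2a model will not depend on the figure used in planning.

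**Conclusion.** No change is needed. The 91% figure has not been shown to be wrong, and the four-week effect has not been shown to be smaller than the acute one. What is missing is detail in the justification: which test the figure refers to, its alpha, effect metric and session correlation, and the fact that the H2a effect is extrapolated. Writing these down would leave the 80 participants, both mixed models, the estimates and the conclusions unchanged.

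The remaining uncertainty about H2a power is real. At 75% of the assumed effect it is 70% on the change-score scale starting from exactly 0.747, and 91% with f = 0.25 and a correlation of 0.5. Both figures assume two-sided 0.05 and 40 evaluable per arm, and both rest on inputs the documents do not give. A careful reader of a null H2a should look at its estimate and precision, not at the planning power.

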13.0 Regulatory Requirements

13.1 Informed Consent

- During the initial assessment, the nature of the research project will be described to participants. A written summary, in lay terms, of the research project will be provided to the participants in the written informed consent document that the participants will review. The consent document will inform

the participants of the voluntary nature of the study procedures, the purpose of the study, the procedures to be followed, the duration of the study, the risks associated with suvorexant, the risks associated with startle and fMRI procedures such as exposure to loud noise bursts, as well as the potential benefits to the community at large. Women will agree that they are not pregnant, nursing, or planning to become pregnant. Participants will be informed that a urine sample for a pregnancy/toxicology screen and a breathalyzer will be obtained at both sessions. Written informed consent will be obtained by the PI or designated research staff and the participant will receive a copy of the signed consent form. Participants will be informed that they can discontinue participation at any time without penalty.

- Each member of the research team will complete the HIPAA and CITI human subjects trainings and will be trained in the research protocol and will have reviewed the informed consent document and assent forms themselves.
- The informed consent document will be stored in a separate locked file cabinet from any other research files in a locked office. Only research staff on this specific research study will have access to the informed consent documents.

13.2 Subject Confidentiality

- All data from subjects will be marked with a research identifier number only and kept in locked cabinets. No data will have subject names on them, except for consent forms, which will be stored separately from other questionnaires in a locked file cabinet. Paper records will be kept in locked file drawers in a locked room, to which only authorized research personnel have access. Confidentiality of subject's records is assured by assigning each subject a research identifier number/code, and such data, as well as fMRI and startle data, are stored in computer files (except for a single tracking file) without reference to name, or any other type of personally identifiable information. Data that may be reported in scientific journals will not include any information that identifies any person as a subject in this study.
- Location and storage of computer files, which will store the startle/fMRI data: These files will be stored on the lab server.
- Single tracking file: This file is a password-protected master key database, which links the participant with unique participant codes; it is stored on the password-protected server, described above, and kept separate from study data. The information in this file could be used to *indirectly* identify participants. Only research study personnel directly involved with the project (e.g., the PI, her research assistants and the project manager) will have access to this file. If any member of the research study leaves, his or her access to the network will be removed immediately, thereby terminating access to this file and other files associated with the study. The record

linking participants to the research codes will be destroyed 6 years after study completion, thereby anonymizing the data.

- Limits of Confidentiality on Clinical Information: Confidentiality is limited, however, when a danger to self or others is present. If the subject is discovered to be acutely homicidal or suicidal during the evaluation period, the subject will be evaluated for hospitalization in a mental health facility (either voluntarily or involuntarily as necessary). If, for whatever reason, the subject is not hospitalized when it is determined that he/she is either homicidal or suicidal (e.g., we receive a phone call from the subject or another person) the police may be alerted to bring the subject to a psychiatric emergency room.
- Confidentiality of Drug Tests Prior to Scans or Assessment: The results of the urine drug and pregnancy screens will remain confidential. The only individuals who will have knowledge of the results of these tests are research staff directly working on the project.
- The only PHI we are collecting in this study include the participants name and contact information (phone number, email address, home address). The reasons that we are collecting this information include: the participants name for the informed consent document, phone number and email address to schedule lab appointments.

